suggestive of cervical carcinoma (i.e. high grade intra-epithelial lesions) will undergo colposcopy with biopsy, and may potentially be eligible for randomization upon confirmed histology results. If a subject with high grade intraepithelial lesions detected on study-related Pap smears is later found to have normal or ASCUS on a follow up Pap smear (study related or not) that occurs prior to or in lieu of a colposcopic evaluation, the subject will still be required to have a study related colposcopy and biopsy.

Subjects who have biopsy-confirmed CIN 2, 3 or CIS will be eligible for the randomization and treatment portion of the study. They will be presented with the consent information upon receipt of biopsy result. Subjects with biopsy results suggestive of cervical carcinoma will be exited from the study and referred for further evaluation and management at KNH. Subjects with CIN I biopsy results will be asked to return to the clinic for repeat Pap smear in 6 months and will remain in the study. If a subject receives three consecutive CIN I histology results, she will be offered LEEP treatment by the study doctor. These participants will be treated and followed the same as other non-randomized LEEP participants.

Of note: Women with normal or with ASCUS Pap smear results (that are exited from the study) will be referred for subsequent cervical screening follow-up at the Hope Center Cervical Cancer Screening Program (CCSP). This program is administered by the Coptic Hospital and is supported by the Coptic Mission, PEPFAR, and other donor funding. The CCSP offers free cervical cancer screening to HIV-positive women enrolled in the Coptic Hope Clinic. Currently, a single visit ‘screen-and-treat’ strategy for cervical cancer prevention and treatment will be used. The screen-and-treat method involves visual inspection of the cervix followed by treatment of precancerous lesions by cryotherapy at the same visit. Patients who cannot be treated with cryotherapy are referred to KNH for subsidized cervical

care and treatment. As all study subjects are drawn from the Coptic Hope HIV clinic, they are all eligible to be screened, treated, and followed at the CCSP.

If a woman exited from her normal or ASCUS Pap smear result prefers to rescreen with the study, she may be re-enrolled using the re-enrollment consent form.

Study Procedures

1. SCREENING visit (at least 2,400 patients) (see Study Flow Diagram I, Enrollment)

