be eligible to re-enroll in the study and obtain a study related screening pap smear, approximately 12 months after their last normal/ASCUS study related pap smear.

- Women found with unsatisfactory results will have their Pap smear repeated.
- Women with LSIL will be offered Colposcopy. According to the 2012 ASCCP guidelines, participants found with LSIL in the absence of HPV co-testing should be recommended colposcopic evaluation and biopsy.
- Any patient who receives a cytological diagnosis of high-grade intraepithelial lesion (HSIL and ASC-H, and HSIL-invasion-not-ruled-out or SCC) (~18% of the patient population or approximately 400 patients), will be recommended to undergo colposcopy as per 2012 ASCCP guidelines. If a subject with high grade intraepithelial lesions detected on study-related Pap smears is later found to have normal or ASCUS on a follow up Pap smear that occurs prior to or in lieu of a colposcopic evaluation, the subject will still be required to have a study-related colposcopy and biopsy. Prior to participating in any cervical procedure, including biopsy, women will undergo a rapid pregnancy test. Pregnant subjects will be exited from the study and followed-up in the CCSP. These women will also be referred for prevention of mother-to-child transmission (PMTCT) care at Hope Center. If the pregnancy result is negative, they will be referred to the study doctor for colposcopy-directed biopsy which will clarify the extent and severity of disease. Results of the colposcopic examination will be entered in the “Colposcopy” questionnaire (see Study Flow I). For patients who have glandular epithelium abnormalities (AGC) on Pap or squamous epithelium abnormalities without visible lesions on colposcopy, endocervical sampling with curettage will be performed in order to identify possible abnormalities in the endocervical canal.

- After undergoing biopsy, women will be given free condoms and advised to abstain from sexual activities for at least 10 days.
3. 6-8-week visit for RANDOMIZATION (~400 patients) (see Study Flow II)
- Subjects who have undergone biopsy will return four to six weeks later for a follow-up visit to be given the results of the biopsy. Biopsy results will be entered in the “Treatment” questionnaire.

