5. Six, twelve, eighteen, and twenty-four months after randomization visits for RECURRENCE (approximately 400 patients) (see Study Flow II)

- After the 9-11-week visit, randomized participants and those who undergo LEEP but are not randomized because their lesions are not amenable to cryotherapy will return at 6, 12, 18, and 24 months after treatment is administered. At the 24 month visit, the subject will be exited from the study. At these 6-month interval visits, the following will be performed in order:
 - Pap smear to detect recurrence of cervical intraepithelial lesions
 - Same Pap smear swab will be used to assess the presence of Human Papillomavirus (HPV)
 - Blood (5 mls) will be drawn to check for CD4 count
 - “Pap Smear” questionnaire completed
- Pap smear results that are normal, ASCUS, will be filed in the participants file and disclosed at the next scheduled follow-up visit. If pre-cancerous lesions by cytology have recurred then patient will be contacted to return to the study clinic to undergo colposcopic directed biopsy prior to treatment. Results of the colposcopic examination will be entered in the “Colposcopy” questionnaire..
 - If histology-confirmed lesions can be treated by LEEP, then the patient will receive a free LEEP and “Treatment” questionnaire will be filled.
 - If histology-confirmed lesions are too large or cancerous for LEEP then patient will be referred to KNH for subsidized care at this government

hospital. The study will not pay for this treatment. Patients will be given follow-up appointments in the study clinic after referral to determine outcomes.

- Phone calls and home visits will be performed sequentially in the case of a subject who has been lost to follow-up (LTFU) after screening or randomization (see LTFU section). LTFU will be prepared and discussed at weekly clinic meetings. Written reports will be prepared from these meetings and sent to co-investigators. Home visits will be performed by community health workers trained to be discreet in their approach to finding patients. They will not wear clothes that would identify them as health workers and will only use public transportation or unmarked private vehicles. They may ask about the participant's health or whereabouts.

6. Specimen transportation

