 Sores	 Normal
 Other (Specify) _____	
7. Were there any perineal warts on external genital exam? Yes No
If yes, specify
 - a. Size _____ mm
 - b. Number of warts _____
 - c. Location of warts _____
8. Did the cervix appear abnormal on gross pelvic exam? Yes No
If yes, tick all that apply

 Abnormal discharge	 Warts
 Bleeds easily on touch	 Cervicitis
 Visible lesion	 Condylomata

- Bloody discharge Ulcers
- Fungating mass
- Leukoplakia Cervical polyp
- Bartholian cysts Blisters
- Overt cervical cancer Other abnormality, specify

9. Did you palpate the uterus? Yes No
If yes, then specify

- a. Estimated uterine size ___ . ___ cm
- b. Was the uterus tender? Yes No
- c. Were there possible fibroids? Yes No

10. Was there any adnexal tenderness? Yes No
If yes, specify location Right Left Both

C: Pap

11. Were you able to take an adequate Pap smear? Yes No

- a. If no, specify why
- Patient discomfort
- Excessive bleeding
- Excessive discharge or inflammation
- Other, specify

D: DIAGNOSIS

12. Normal exam Yes No
13. Candidiasis Yes No
14. Cervicitis Yes No
15. Pelvic inflammatory disease Yes No
16. Vulval warts Yes No
17. Vaginal warts Yes No
18. Genital ulcerations Yes No
19. Lower genital tract infection Yes No
20. Other Yes No
If others, specify

E: OTHER

21. Did you give any treatment to the participant? Yes No
If yes, specify (treatment)

22. Did you give referral to the participant? Yes No
If yes, specify (diagnosis and referral institution)

23. Comment.

COLPOSCOPY

Study ID Number ___ ___ ___

Interviewer Number ___ ___

Date of interview (day/month/year) ___ ___ / ___ ___ / ___ ___ ___ ___

Visit (tick one) Initial Visit Month 6 FU Month 12 FU Month 18 FU Month 24 FU LSIL FU CIN 1 FU Other, specify _____

A: PAP SMEAR DIAGNOSIS

1. What date was the Pap smear performed?
2. What was the Pap smear diagnosis (tick all that apply)?
 - No dysplasia (NIL)
 - ASCUS
 - LSIL (CIN 1)
 - HSIL (CIN 2 & 3)
 - ASC-H
 - Invasive carcinoma
 - ACG (Atypical Glandular Cells)
 - Cervicitis
 - Yeast infection
 - Indeterminate/insufficient sample
 - Other, specify _____
 - Unknown, specify reason _____
3. Is cervical biopsy with colposcopy indicated based on Pap smear cytology?

Yes No

If no, [skip to Q24 and](#) fill exit form where necessary

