If yes, and colposcopy had been done previously, skip to Q24.

If yes and colposcopy had not been done previously, do a pregnancy test

4. Result of pregnancy test: Pregnant Not Pregnant

(If pregnant fill exit form, If not pregnant refer for colposcopy)

Not pregnant

B: PHYSICAL EXAMINATION

5. Temperature ___ °C

6. Is there inguinal node enlargement Yes No

7. Is there abdominal tenderness Yes No

8. Are there any abdominal masses Yes No

9. Were there any other abnormalities found on general physical exam Yes No
If yes, specify

C: PELVIC EXAMINATION

10. What was found on the external genital exam (tick all that apply)?

Abnormal visible discharge at introitus Ulcers

Excoriations Vesicles

Oedema Papules

Sores Normal

11. Were there any perennial warts on external genital exam? Yes No
If yes, specify

d. Size ___ mm

e. Number of warts ___

f. Location of warts _____

12. Did the cervix appear abnormal on gross pelvic exam? Yes No
If yes, tick all that apply

Abnormal discharge Warts

Bleeds easily on touch Cervicitis

Visible lesion Condylomata

Bloody discharge Ulcers

Fungating mass

Leukoplakia Cervical polyp

Blisters

Overt cervical cancer

13. Did you palpate the uterus? Yes No
If yes, the specify

a. Estimated uterine size ___ . ___ cm

b. Was the uterus tender? Yes No

c. Were there possible fibroids? Yes No

d. Was there any adnexal tenderness? Yes No

d(i) If yes, specify location Right Left Both

D: COLPOSCOPIC BIOPSY

15. Did you see the entire squamocolumnar junction (SCJ)? Yes No

16. Was it a satisfactory colposcopy? Yes No

If no, specify

17. Were there colposcopic findings within the transformation zone? Yes No
If yes, specify (tick all that apply)

Flat acetowhite epithelium

Micropapillary or microconvoluted acetowhite epithelium

Leukoplakia

Punctation

Mosaic

Atypical vessels

Iodine-negative epithelium

Lesion extended into endocervix

18. Draw SCJ (acetowhite, punctation, mosaics, atypical vessels, and other lesions):

19. Were there any other colposcopic findings? Yes No

If yes, specify (tick all that apply)

Mucosal bleeding easily induced

Purulent cervicitis

Opaque discharge

Yellow discharge

Other, specify:

20. Were there colposcopic findings consistent with invasive carcinoma?
Yes No

E: COLPOSCOPY DIAGNOSIS

21. Is patient eligible for cryotherapy if necessary? Yes No
If no, indicate reason (tick all that apply)

- Lesion >75% of cervix
- Lesion is larger than cryoprobe tip
- Lesion suspicious for cancer

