- Polyp or anatomic defect preventing access to cervix
- Previous treatment with cryotherapy in this study
- Other, specify

22. What was your diagnosis based on colposcopy examination (tick all that apply)?

- Normal colposcopic findings
- Unsatisfactory, specify:
- Inflammation/infection, specify
- Leukoplakia
- Condyloma
- LSIL (CIN 1)
- HSIL (CIN 2 & 3)
- Invasive cancer
- Other, specify:

D: SPECIMEN COLLECTION

23. Was a biopsy taken? Yes No
- a. If yes, how many biopsies were taken ___
 - b. Draw: (mark site(s) with an 'X' on colposcopy drawing)
 - c. If no, specify why biopsy was not taken

E: Treatment

24. Was any treatment given to the patient? Yes No
If yes, specify treatment
25. Was a referral given to the patient? Yes No
If yes, specify diagnosis, and the referral institution

26. Comments:

RANDOMIZATION

Study ID Number _____ Hope ID Number _____

Randomization Number __ Interviewer Number _

Date of interview (day/month/year) ____/____/____

A: CURRENT MEDICAL HISTORY

1. Do you have pain when passing urine? Yes No Other, specify Refused Don't know
2. Do you have any lower abdominal pain? Yes No Other, specify Refused Don't know
3. Do you have any abnormal vaginal discharge? Yes No Other, specify Refused Don't know
4. Have you noticed any growths around your vagina? Yes No Don't know Other, specify Refused Don't know

B: REPRODUCTIVE HEALTH

5. How old were you when you had your first menstrual period? ____ Don't know refused Other, specify
6. Date of last menstrual period (day/month/year) ____/____/____ Don't know refused Other, specify
7. Do you have history of abnormal vaginal bleeding Yes No Don't know Refused Other, specify

If yes specify the type of bleeding

- Irregular
- Heavy
- Menorrhagia Other, specify
- Don't know
- Refused

8. Have you ever used any form of family planning method? Yes No
Don't know

Refused

Other, specify _____

If yes, specify (tick all that apply)

Injectable IUCD Natural

Condoms OCP Norplant/ Implant

BTL others, specify _____

9. Are you using any form of family planning method now?

Yes No Don't know Refused

Other, specify _____

If yes, specify (tick all that apply)

Injectable IUCD Natural

Condoms OCP Norplant/ Implant

BTL others, specify _____

10. How many times have you been pregnant? ___ ___ Refused Don't know
Other

11. How many times have you had live births? ___ ___ Refused Don't know
Other

12. How many abortions, miscarriages, and/or stillbirths have you had? ___ ___

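### Colposcopy form Q3 does not tie an earlier colposcopy to the current Pap result, so read literally it sends women recalled for repeat colposcopy past the pregnancy-test and colposcopy items

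*Combined protocol and SAP*

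**What the plan says.** Section A of the Colposcopy form takes the date of the Pap smear (Q1), its result (Q2), and whether cytology indicates colposcopy with biopsy (Q3). Under Q3, a yes answer splits in two: "If yes, and colposcopy had been done previously, skip to Q24", and "If yes and colposcopy had not been done previously, do a pregnancy test". Q4 records the pregnancy result and says what to do next: exit if pregnant, refer for colposcopy if not. Q24 is the treatment item near the end of the form.

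The form is not confined to first visits. Its visit boxes read "Initial Visit Month 6 FU Month 12 FU Month 18 FU Month 24 FU LSIL FU CIN 1 FU".

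Three protocol rules bear on this:

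- Study Procedures, item 2 (results visit): "Prior to participating in any cervical procedure, including biopsy, women will undergo a rapid pregnancy test".
- Study Procedures, item 5 (recurrence visits): women whose cytology shows recurrence are called back for colposcopic biopsy before treatment, and "Results of the colposcopic examination will be entered in the “Colposcopy” questionnaire".
- Study Population & Recruitment: "If a subject receives three consecutive CIN I histology results, she will be offered LEEP treatment by the study doctor". Repeat biopsy in the same woman is therefore planned.

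**The concern.** The skip turns on whether a colposcopy has ever been done. In follow-up the answer is always yes, because colposcopy-directed biopsy comes before randomisation, before non-randomised LEEP, and before a CIN 1 classification. On the literal wording, the women for whom the follow-up boxes were printed are routed around the items they are being recalled to complete.

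Two things are at stake. One is the form's prompt for, and record of, a pregnancy test before a repeat biopsy or LEEP. The other is the record of follow-up colposcopy findings, including Q23c, "If no, specify why biopsy was not taken", which explains a recalled woman with no biopsy result.

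**Working it through.** The plan states no figure on this point, so the check is a trace of the skip against the protocol.

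**1. The branches of Q3.**

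| Colposcopy indicated? | Earlier colposcopy? | Instruction |
|---|---|---|
| No | – | Go to Q24, exit form where needed |
| Yes | Yes | Go to Q24 |
| Yes | No | Pregnancy test, then Q4 onward |

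**2. A treated woman with HSIL at Month 12.** Q3 is yes. She had a colposcopy before treatment, so the second row applies and she goes to Q24. Study Procedures item 5 recalls this same woman for biopsy and puts the findings on this form.

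**3. A CIN 1 follow-up woman.** Three consecutive CIN 1 histologies need three biopsies. The second and third both follow an earlier colposcopy (3 − 1 = 2), so both would be skipped.

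**4. Items bypassed.** These are Q4 (pregnancy result), Q5–Q13 (physical and pelvic examination) and Q15–Q23 (colposcopic findings, cryotherapy eligibility, diagnosis, biopsy taken or why not). There is no Q14. Q5–Q13 largely repeat Q1–Q10 of the Pap Smear form, so the items that matter are Q4 and Q15–Q23.

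**5. Internal evidence.** Q21 offers, as a reason for not being eligible for cryotherapy, "Previous treatment with cryotherapy in this study". A woman to whom this applies has already had a colposcopy, so under the literal skip she never reaches Q21 and the option is effectively unreachable. This points to a drafting slip and not to a deliberate choice.

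**6. What is recorded elsewhere.** When a recurrence is treated by LEEP, item 5 also requires the Treatment form. Its Q5 (amenability to cryotherapy, with reasons), Q9 (squamocolumnar junction seen) and Q10 (drawing) overlap Colposcopy Q21, Q15 and Q18. Biopsy and endocervical curettage have their own histology reports with Month 6 to 24 boxes, and item 2 calls for curettage when squamous abnormality has no visible lesion. What remains uncovered is mainly the colposcopic detail in women who are not treated, and the reason when neither specimen was taken.

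**7. The pregnancy-test record.** The Enrollment and Shedding forms ask only whether the woman thinks she may be pregnant. The Pap Smear and Follow-up forms have no pregnancy item. In the study forms shown, Q4 is the only field for a test result (the start of the Treatment form is not in the text available). The Personnel section gives laboratory staff urine for pregnancy to collect and a lab book to track specimens and results. However, the specimen-collection and laboratory-results lists under Data Management, Databases, name neither urine nor pregnancy tests. The lab book is therefore a weak backstop.

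**8. Electronic capture.** Data Management, Entry, lists the forms completed on paper, and Colposcopy is not among them. The section on ranges and validity rules says skip patterns were built into the electronic forms. This skip may therefore have been programmed, but the live logic is not in the documents.

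**9. Scale, as an assumption only.** The documents give no number of repeat colposcopies. Applying the sample-size rates in Statistical Methods (4% and 14%) to follow-up smears in 200 women per arm gives 0.04 × 200 + 0.14 × 200 = 8 + 28 = 36 possible recalls among 400. With the 20% loss allowed for, 0.04 × 160 + 0.14 × 160 = 6.4 + 22.4 = 28.8, about 29 among 320. Recalls for low-grade cytology, CIN 1 follow-up women and non-randomised LEEP women would add an unknown number.

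**The case against.** The strongest reply is that context supplies the missing qualifier. Q1 and Q2 tie each form to one dated smear, and Q3 asks about that smear's cytology, so the natural sense is that colposcopy was already done for this result. There is a visit where that sense is needed: after a quality-control re-read, Study Procedures item 9 has a Colposcopy form completed at the disclosure visit, when colposcopy may already have taken place. A reading that makes a Q21 option unreachable is also one a sensible user would reject.

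Much of this stands. The narrower meaning is probably what was intended. It is also true that a missing prompt is not an instruction to omit a test: the pregnancy-test rule has no exception for repeat colposcopy, and item 5 independently names this form for follow-up findings. But the form is what staff work through, the narrower meaning is nowhere on it, and the wording that is there gives the wrong route.

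A reader might go further and infer that pregnancy tests were missed or recurrences lost. The documents do not support that. They do not show whether staff followed Q3 literally or how the electronic form behaved, and Data Management also describes checks against leaving required questions unanswered.

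**Conclusion.** The point holds as a minor form error. The Q3 skip is over-broad as written. Taken literally, it is inconsistent with the pregnancy-test rule in Study Procedures item 2 and the recording rule in item 5. The consequence is a possible loss of a safety prompt and of some follow-up colposcopy detail in recalled women, partly covered by the Treatment form and the histology reports.

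The conclusion rests on the printed wording. It assumes nothing about actual conduct. The 29 to 36 possible recalls depend on borrowing the planning rates and should not be read as women mis-routed.

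Nor should a reader infer an effect on the trial's comparison. The analysis in Statistical Methods uses Pap smear results, which are recorded before this form is opened. Sample size, power and type I error are not involved.

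**What to change.** Reword the two lines under Q3:

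- *If yes, and colposcopy has already been done for this Pap result, skip to Q24.*
- *If yes, and colposcopy has not been done for this Pap result, do a pregnancy test.*

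Check the programmed skip on the electronic form and correct it if it follows the printed wording. Then list completed follow-up Colposcopy forms with Q3 = Yes and Q4–Q23 blank, and compare them with the laboratory records and with the colposcopic biopsy, endocervical curettage and LEEP histology reports.

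The cost is two lines on one form, one skip to check, and one data listing. No new procedure is needed, since the protocol already requires both the test and the record.

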18.1. How was HIV detected? (tick only one)

- At the occasion of a VCT: Yes
- During pre-natal check-up: Yes
- Because of a sickness, specify: _____ Yes
- Other, specify: _____
- Don't know:
- Refused:

19. Are you currently on antiretroviral medications? Yes No
 Don't know
 Refused
 Other, specify _____

If yes,

a) specify current medications: _____

b) original start date: ____ / ____ / ____ Don't know

c) Do you know why you were started on antiretroviral medication?

- because of sickness, specify: _____ Yes
- because of low CD4 count: Yes
- because of high viral load: Yes
- Other, specify: _____
- Don't know:
- Refused:

20. Comment

4. Is patient indicated for LEEP or cryotherapy treatment based on histopathology?

Yes No

If no, continue to 14

5. Is patient's lesion amenable to cryotherapy? Yes No (If yes, go to question 6)

5(i) If no, indicate reason (tick all that apply)

- Lesion >75% of cervix
- Lesion is larger than cryoprobe tip
- Invasive cervical cancer on histology
- Lesion suspicious for cancer
- Polyp or anatomic defect preventing access to cervix
- Patient declines procedure
- Other, specify

5(ii) If no, is patient's lesions amenable to LEEP? Yes No

If yes, skip to 7

If no, skip to 14

6. Was patient randomized to LEEP or cryotherapy today? Yes No
If yes, to which treatment? LEEP Cryotherapy

If no, why?

- Patient refuses
- Patient not eligible for treatment, specify reason
- Other, specify

C: TREATMENT

7. Did you perform LEEP or cryotherapy today? (tick one)
LEEP Cryotherapy Neither, explain

(If neither, explain, skip to Q14)

- 8. Did you visualize the full extent of lesion? Yes No
- 9. Was the squamocolumnar junction fully visualized? Yes No
- 10. Draw position of lesion and treatment performed:
- 11. Did the patient experience any pain during the procedure? Yes No
- 12. Was analgesia provided? Yes No
- 13. Were there any complications? Yes No

If yes, specify

14. Was any antibiotics given? Yes No

If yes, specify

D: OTHER

15. Was the patient referred for further treatment at another institution? Yes

No

If yes, specify institution and reason

16. Was treatment or a referral given for something other than cervical disease? Yes No

If yes, specify (give diagnosis and treatment)

17. Comments

ADDRESS AND INTAKE

Study ID number _ _ _ _

Interviewer number _ _ _ _

Date of interview (day/month/year) _ _ _ / _ _ _ / _ _ _ _ _ _

Format(tick one)

 New Update (fill only updated info)

A. PERSONAL INFORMATION

1. What is your name?
 - a. First name
 - b. Middle name
 - c. Last name
2. How are you called in your home area?
3. What is the current physical location where you live?
 - a. District
 - b. City
 - c. Village
 - d. Estate
 - e. Plot number
 - f. Door number
 - g. Road name
4. Public Transportation to the house:
 - 4a. Type: F Bus F Boda boda F Matatu F Taxi F Other (specify)
 - 4b. Route number:
 - 4c. Stage Name
 - 4d. General Name of the Area
5. Walking directions to house from the stage?
6. Landmarks that aide in locating the household: (Names of schools, churches, businesses etc.)
7. Can you be reached by phone? Yes No
If yes,
 - 7 (i)What is the phone number 1?
 - 7 (ii)What is the phone number 2?
 - 7iii. Who carries the phone (tick one) self other, specify

B. SIGNIFICANT CONTACT

8. Is there another person who is ware of your HIV status that we can contact through phone if we are unable to reach you directly?
If no, skip to 9.
9. What is the name of this contact person?
a. First name
b. Middle name
c. Last name
10. What is the relationship of this person to you?
11. (a)What is the phone number 1?
(b) What is the phone number 2?

C. UPCOUNTRY INFORMATION

12. Do you have an upcountry home? Yes No
If no, skip to 19
13. What is the physical location of your upcountry home?
a. District
b. City
c. Village
d. Estate
e. Plot number
f. Door number
14. Specific directions to residence
15. Is there person located in your upcountry home whom we can contact if we are unable to reach you directly? Yes No
If no, skip to 19
16. What is the name of this contact person?
a. First name
b. Middle name
c. Last name
17. What is the relationship of this person to you?
18. Does this contact have a phone number? Yes No
If yes, specify: phone number 1, phone number 2

D. OTHER

Comment:

SHEDDING

Study ID Number ___ ___ ___

Interviewer Number ___ ___

Date of interview (day/month/year) ___ ___ / ___ ___ / ___ ___ ___ ___

Visit (tick one) Week 1 FU Week 2 FU Week 3 FU Other, specify _____

A: MEDICAL HISTORY

1. Has the patient experienced any lower abdominal pain since the last visit?

Yes No

If yes, indicate:

a. Duration ___ ___ days

b. Severity (scale from 1 to 5; 5 being most severe) ___ ___

2. Has the patient experienced any vaginal bleeding since the last visit?

Yes No

If yes, indicate:

a. Duration ___ ___ days

b. Volume

 Stain pants Requires sanitary pad Other, specify

3. Has the patient experienced any vaginal discharge since the last visit?

Yes No

If yes, indicate:

c. Duration ___ ___ days

d. Color

 Yellow Brown White Clear

Other, specify

e. Smell

Malodorous

No odor

Other, specify

f. Volume

Stain pants

Requires sanitary pad

Other, specify

4. Has the patient experienced any fever after the last visit?

Yes No

If yes, specify duration ___ days

5. Did the patient seek medical care for these or other complaints?

Yes No

If yes, specify what complaint prompted the participant to seek care:

Abdominal pain

Fever

Vaginal Bleeding

Vaginal discharge

a. Other, specify

If yes, specify where the participant sought care:

Study clinic

Hope Center

Coptic Hospital

KNH

b. Other, specify

6. Was the participant's condition possibly due to a study procedure? (Ask if any of questions 1-4 is yes)

Yes No

If any question 1-4 is Yes and the condition is not expected as per study protocol, or is more severe than expected, fill an AE form.

7. Date of last menstrual cycle (dd/mm/yyyy)

8. Have you ever had vaginal sex since treatment? Yes No Refused

Other (specify) _____

8 (a). If yes, how many times? ___

8(b) If you have had vaginal sex since treatment, how often did you use condoms during sex?

Always (100%) Most of the time (75-99%)
 Half of the time (50%-74%) Sometimes (25-49%)
 Rarely (1-25%) Never (0%)
 Refused Don't know Other, specify _____

9. Do you think you may be currently pregnant? Yes No

10. Are you currently on antiretroviral medications?

Yes Refused Other, specify

No Don't know

If No, Refused, or Don't Know, skip to Q14

If yes, specify current medications and original start date.

- d4t, 3tc, nvp
- d4t, 3tc, efv
- azt, 3tc, nvp
- azt, 3tc, efv
- Other specify

Original ARV start date (dd/mm/yyyy)

11. During the last 7 days, how many antiretroviral pills did the patient MISS taking?

12. During the last 30 days, how many antiretroviral pills did the patient MISS taking?

(If Q11 and Q12 patient did not MISS taking any pills skip to Q14)

13. If the patient missed any doses, please specify reasons (check all that apply)

- Toxicity/ side effect
- Share with others
- Forgot
 - c. Felt better
- Too ill
- Stigma, disclosure or privacy issues
- Drug out of stock
- Patient lost or ran out of pills
- Delivery /travel problem
- Inability to pay
- Alcohol
- Depression
 - d. Other specify

B: DIAGNOSIS

14. Is there any new infection that was related to the procedure since the last visit?

Yes No

If yes, specify and fill an Adverse Event questionnaire:

15. Were there any new complications diagnosed today related to the treatment?

Yes No

If yes, specify and fill an Adverse Event questionnaire:

C: TREATMENT

16. Was any treatment provided today? Yes No

If yes, specify

17. Was the patient referred for further cervical treatment at another institution?

Yes No

17 (i) If yes, specify institution

17(ii) If yes, specify reason for referral

D: SPECIMEN COLLECTION

18. Did you collect cervical HIV swab? Yes No
 If no, specify reason:

19. Did you collect blood? Yes No
 If no, specify reason:

E: ACCEPTABILITY OF TREATMENT

20. Please complete the items listed below by placing a checkmark on the box next to each question that best indicates how the client feels about the treatment she received.

	Strongly Disagree	Disagree,	Neutral,	Agree	strongly agree
(i) I find this treatment an acceptable way of dealing with cervical lesions					
(ii) I would be willing to use this procedure if I were to develop more lesions					
(iii) I would recommend this procedure to someone with cervical lesions					
(iv) overall, I have a positive reaction to this treatment					

F: OTHER

22.

—

23.

24. Comments:

PATIENT CONTACT

Study ID Number ___ ___

Interviewer Number ___ ___

Date of contact (day/month/year) ___ ___/___ ___/___ ___

1. Date of last Hope clinic visit (day/month/year)
2. Date of last study clinic visit (day/ month/year)
3. Was patient or patient contact reached by phone or home visit?
 Phone Home visit Other, specify

4. Did you talk to the patient or patient contact?

- Yes, talked to patient (*Go to 6*)
- Yes, talked to patient contact (*Go to 5*)
- No (*Go to 4*)

5. If talked to patient contact, who was the source of information (tick one)

- Clinician / clinic staff Mother or Father Neighbor
- Spouse or Partner Employer Caregiver
- Family member / Relative Friend Treatment supporter
- Other (specify)

5a. Did the source of information have credible knowledge for whether the patient was alive or dead?

- Yes, credible and patient confirmed alive (*Go to 4*)
- Yes, credible and patient confirmed dead (*Go to 7 and complete Verbal Autopsy form*)
- Source did not know whether patient was dead or alive (*Go to 4*)
- Source not credible (*Go to 7 and complete Verbal Autopsy form*)

6. Reasons for missed study appointment (tick all that apply)

- N/A, did not reach patient or patient contact
- Unable attend because health problem
- No longer willing to be in study
- Family problems
- Wait time too long in clinic
- Client will go to faith healer
- Conflict with work
- Unwilling to disclose
- Financial problems
- No longer willing attend Hope Clinic
- Client moved or relocated
- Other (specify)

7. If talked to patient, did the patient wish to remain in the study?

- Yes (*Go to 7a*)
- No (*Go to 8 and complete Exit Form*)
- N/A, did not talk to patient (*Go to 9*)

7a. Did the patient schedule a study appointment? Yes No (*If Yes go to 7b, If No go to 7c*)

7b. If yes, date of scheduled appointment (DD/MM/YYYY)

7c. If no, why did the patient not schedule an appointment (tick all that apply)

- Unable to attend because of health problems
- Family problems
- Conflict with work
- Financial problems
- Client moved or relocated
- Client lives too far away
- Other (specify)

8. If the patient does not wish to return to the study, specify why (tick all that apply)

F Not willing to attend Hope Clinic

F Not willing to be in study

F Attend clinic closer to home

F Wait time too long

F Conflict with work

F Financial problems

F Unwilling to attend because of health problems

F Family problems

F Client will go to a faith healer

F Not willing to disclose HIV status

F Referred else where

F Other (specify)

F Unknown

9. Comments

VERBAL AUTOPSY

Study ID Number _____

Interviewer Number _____

Date of interview (day/month/year) ____/____/____

1. Age at death FF years

2. Date of death (DD/MM/YYYY) FF/FF/FFFF

3. Place of death

4. The information source for the cause of death was (tick all that apply)

Partner/spouse

Mother or Father

Friend

Hospital records/staff

Other family member/relative

Care giver

Neighbor

Unknown

Other (specify)

5. Was the deceased seeking other medical treatment (other than Hope Center) during the last 3 months before his/her death? Yes No Unknown *If yes go to*

5a, if no go to 6

5a. If yes, where specifically was the deceased receiving other medical care?

Name of facility: _____

5b. What type of care was the deceased receiving at the these other facilities? (Tick all that apply)

General medical care

TB

STD

HIV/AIDS

Malaria

Other infectious disease(s)

Other care (specify all types of care received: _____)

6. Respondent’s detailed account of the illness of the deceased:

7. Did a health care worker tell you the cause of death? F Yes F No F Unknown
If yes go to 7a, if no go to 8

7a. What did the health care worker say was the cause of death? _____

8. Did s/he have any operation for the illness? F Yes F No F Unknown
If yes go to 8a, if no go to 9

8a. How long before the death was the operation? _____ days

8b. On what part of the body was the operation?

F Abdomen F Chest F Head F Other(Specify _____)

9. Has spouse or other sexual partner(s) of the deceased died in the past 5 years?

F Yes F No F Unknown
If yes go to 9a, if no go to 10

9a. If yes, what is the believed cause(s) of death of the partner(s)

9a1. Partner 1: _____

9a2. Partner 2: _____

Injury/accident/suicide

10. Did s/he suffer from any injury or accident that led to her death? F Yes F No F Unknown

If yes go to 10a, if no go to 11

10a. What kind of injury or accident did the deceased suffer?

Road traffic accident Fall Drowning Poisoning

Burns Violence/assault

Other: _____

Unknown

10b. Was the injury or accident intentionally inflicted by someone else? Yes No Unknown

10c. Do you think that s/he committed suicide? Yes No Unknown
Skip to Q.12

11. Did s/he suffer from any animal/insect bite that led to her/his death? Yes No Unknown

11a. If yes, what type of animal/insect? _____

History of previously known medical conditions

12. Did the deceased suffer from any of the following conditions?

- a. High blood pressure Yes No Unknown
- b. Diabetes Yes No Unknown
- c. Asthma Yes No Unknown
- d. Epilepsy Yes No Unknown
- e. Malnutrition Yes No Unknown
- f. Cancer Yes No Unknown

f1. If yes, specify type of cancer or site: _____

g. Tuberculosis Yes No Unknown

h. Any other medically diagnosed illness? Yes No Unknown

h1. If yes, specify: _____

13. Signs, symptoms, and their severity during the last illness:

Symptom/ Signs	Symptom present?	If present, duration of symptom
a. Fever	FNo F Yes	F ≤2 weeks F >2 weeks F Unknown
b. Loss of weight	FNo F Yes	F ≤2 weeks F >2 weeks F Unknown
c. Diarrhea	FNo F Yes	F ≤2 weeks F >2 weeks F Unknown
d. Vomiting/associated abdominal pain	FNo F Yes	F ≤2 weeks F >2 weeks F Unknown
e. Constipation/associated abdominal pain	FNo F Yes	F ≤2 weeks F >2 weeks F Unknown
f. Cough	FNo F Yes	F ≤2 weeks F >2 weeks F Unknown
g. Cough followed by vomiting	FNo F Yes	F ≤2 weeks F >2 weeks F Unknown
h. Breathing trouble (chest indrawing/difficult/rapid/wheezing)	FNo F Yes	F ≤2 weeks F >2 weeks F Unknown
i. Neck stiffness	FNo F Yes	F ≤2 weeks F >2 weeks F Unknown
j. Unconscious episodes	FNo F Yes	F ≤2 weeks F >2 weeks F Unknown
